10.1.3 Study-specific Adverse Event Definitions

10.1.3.1 Infusion-related Reactions

An *IRR* is any sign or symptom experienced by a patient during the infusion of the IMP or any event occurring on the day of the IMP infusion after the infusion was started.

Clinical manifestations of IRRs vary. Examples of IRRs include anaphylactoid reactions, anaphylaxis, dizziness, flushing, hypotension, nasal congestion, nausea, and syncope.

10.1.3.2 Management of Reactions to Study Drug

There are no specific antidotes to an infusion of Lu AG09222.

A medical emergency should be treated appropriately by the investigator using proper standard of care, according to their typical clinical practice and local guidelines for that emergency condition.

Should a medical condition arise that the investigator believes is related to the study drug, clinical judgement should be used to provide appropriate response including the consideration of discontinuation of study drug. Any events believed to be allergic reactions should be discussed with the medical monitor.

CCI [REDACTED]

[REDACTED]

[REDACTED]

10.2 Pregnancy

Although not necessarily considered an adverse event, a pregnancy in a patient in the study must be recorded on an *Adverse Event Form*, as well as on a *Pregnancy Form* (paper), even if no adverse event associated with the pregnancy has occurred. Pregnancies must be reported to Lundbeck using the same expedited reporting timelines as those for SAEs.

An uncomplicated pregnancy should not be reported as an SAE; hospitalization for a normal birth should not be reported as an SAE. If, however, the pregnancy is associated with an SAE, the appropriate serious criterion must be indicated on the *Serious Adverse Event Form*. Examples of pregnancies to be reported as SAEs (medically important) are spontaneous abortions, stillbirths, and malformations.

If the partner of a man participating in the study becomes pregnant, the *outcome* of the pregnancy should be followed if the partner agrees. The partner must sign a pregnant partner informed consent form to allow the investigator to collect information to report to Lundbeck.

The investigator must follow up on the *outcome* of the pregnancy and report it on a *Pregnancy Form* (paper). The follow-up must include information on the neonate at least up until the age of 1 month.

10.3 Recording Adverse Events

Adverse events (including pre-treatment adverse events) must be recorded on an *Adverse Event Form*. The investigator must provide information on the adverse event, preferably with a diagnosis, or at least with signs and symptoms; start and stop dates (and start and stop time if the adverse event lasts less than 24 hours); intensity; causal relationship to the IMP; action taken; and outcome. If the adverse event is not related to the IMP, an alternative aetiology must be recorded, if available. If the adverse event is an overdose, the nature of the overdose must be stated (for example, medication error, accidental overdose, or intentional overdose). If the intensity changes during the course of the adverse event, this must be recorded on the *AE Intensity Log*.

If the adverse event is *serious*, this must be indicated on the *Adverse Event Form*. Furthermore, the investigator must fill out a *Serious Adverse Event Form* and report the SAE to Lundbeck immediately (within 24 hours) after becoming aware of it (see section 10.4).

If individual adverse events are later linked to a specific diagnosis, the diagnosis should be reported and linked to the previously reported adverse events.

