Recent medication (prescription and non-prescription), herbal remedies, non-pharmacological interventions, vitamin and mineral supplements	√							
Height	√							
Blood sampling for serology (HBsAg, anti-HBs, anti-HBc, and anti-HCV)	√							
Blood sampling for other screening (e.g., β-hCG, FSH)	√							
Urine drug screen and alcohol screen	√							
Inclusion/exclusion criteria	√	√						
Signs and symptoms present at Screening and Baseline (before IMP administration) (recorded on an Adverse Event Form)	√	√						
CCI		√ ^j						
Randomization		√						
Efficacy Assessments								
eDiary daily recording ^{f,g}	√	√ ^j	√	√	√	√ ^{e,k}	√ ^k	√ ^k

Visit Name	Screening	Baseline + IMP		Primary Outcome		Safety Follow-up	Withdrawal ^f	Efficacy Follow-up (telephone contact) ^e
Visit Number	1 SCR	2 BL	3	4 PO	5	6 SFU	WD	EFU
Type of Visit ^x	Clinic	Clinic	Clinic /Tele visit / Home	Clinic /Tele visit / Home	Clinic /Tele visit / Home	Clinic	Clinic /Tele visit / Home	Tele phone
Day/End of Week ^a	-4	0	2	4	8	12		4
Visit Window ^b (days relative to nominal visit)	-2		±2	±2	±2	±5		±2
eDiary compliance check ^{f,h}		✓	✓	✓	✓	✓ ^c	✓	✓
CCI		█	█	█	█	█	█	
	█	█		█	█	█	█	
		█	█	█	█	█	█	
		█		█	█	█	█	
		█		█	█	█	█	
		█		█	█	█	█	
		█		█	█	█	█	
		█		█	█	█	█	
		█	█	█	█	█	█	
		█		█	█	█	█	
		█		█	█	█	█	
		█		█	█	█	█	
		█		█	█	█	█	
		█		█	█	█	█	
		█		█	█	█	█	
		█		█	█	█	█	
		█		█	█	█	█	
		█		█	█	█	█	
		█		█	█	█	█	
Pharmacokinetic Assessments								
Blood sampling for CCI quantification		✓ ^l	✓	✓	✓	✓	✓	
Exploratory Pharmacodynamic Assessments								
Blood sampling for CCI		✓ ^l	✓	✓	✓	✓	✓	
Blood sampling for CCI		✓ ^m		✓				
Blood sampling for CCI		✓ ^m		✓				
Safety Assessments								
Adverse events	✓	✓ ^{m,n,o}	✓	✓	✓	✓	✓	✓
Blood and urine sampling for clinical safety laboratory tests	✓	✓ ^m	✓	✓	✓	✓	✓	
Blood sampling for ADA including NAb		✓ ^m	✓	✓	✓	✓ ^p	✓	
Vital signs (including body temperature), weight, ECGs	✓	✓ ^{m,n}	✓	✓	✓	✓	✓	
Examinations (physical) ^q	✓	✓ ^m		✓		✓	✓	
Examinations (neurological) ^q	✓	✓ ^m				✓	✓	
C-SSRS ^r	✓	✓ ^m	✓	✓	✓	✓	✓	

Visit Name	Screening	Baseline + IMP		Primary Outcome		Safety Follow-up	Withdrawal ^f	Efficacy Follow-up (telephone contact) ^e
Visit Number	1 SCR	2 BL	3	4 PO	5	6 SFU	WD	EFU
Type of Visit ^x	Clinic	Clinic	Clinic /Tele visit/ Home	Clinic /Tele visit/ Home	Clinic /Tele visit/ Home	Clinic	Clinic /Tele visit/ Home	Tele phone
Day/End of Week ^a	-4	0	2	4	8	12		4
Visit Window ^b (days relative to nominal visit)	-2		±2	±2	±2	±5		±2

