- l. Multiple samples for CCI are to be taken relative to IMP infusion: prior to infusion, immediately after the end of infusion (EOI) and 2 hours after EOI.
- m. The following must be collected/completed prior to infusion: vital signs (including blood pressure, pulse, respiratory rate, and body temperature), concomitant medications, substance use, AEs, physical and

- neurological examinations, ECG, blood sampling (for clinical safety laboratory tests, CCI [REDACTED] ADA including NAb, and optional CCI [REDACTED] urine sampling (for clinical safety laboratory and pregnancy tests), CCI [REDACTED] and C-SSRS. Vital signs must be assessed prior to blood sampling.
- n. The following must be collected after infusion: vital signs (including blood pressure, pulse, respiratory rate, and body temperature), AEs and blood sampling for CCI [REDACTED]. Vital signs must be assessed prior to blood sampling.
 - o. Infusion-related reactions must be checked as part of the overall AE collection, during and after infusion, and before the patient is discharged from the site.
 - p. A proportion of patients who complete the Safety Follow-up Visit (Week 12) will be asked to provide additional blood samples for post-study immunogenicity testing at 12-week intervals (potentially up to 12 months relative to the infusion date). The number of patients from whom these samples will be collected will be decided during the study in consultation with the sponsor.
 - q. For the Baseline Visit, examinations must be performed prior to the infusion.
 - r. The CCI [REDACTED] and C-SSRS will be administered by the authorized rater. For this study, the following versions of the C-SSRS scale are used: the “Baseline/Screening” will be used at the Screening Visit and the “Since last visit” version will be used for all subsequent visits.
 - s. CCI [REDACTED]
 - t. An unblinded pharmacist or designee is responsible for receiving, storing, and preparing the IMP. The pharmacist or designee will not be responsible for other aspects of the clinical study where blinding is necessary.
 - u. Patients must be monitored during the infusion and for a period of 2 hours from the EOI. Patients will be requested to stay longer should the investigator or designee determine this is clinically warranted.
 - v. A designated unblinded clinical research associate is responsible for IMP accountability.

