16.9 Safety Analyses

16.9.1 Analysis of Adverse Events

Adverse events will be classified according to the time of onset of the adverse event:

- *pre-treatment adverse event* – an adverse event that starts on or after the date the patient signed the *Informed Consent Form* and prior to the date of first dose of IMP
- *treatment-emergent adverse event* – an adverse event that starts or increases in intensity on or after the date of first dose of IMP

Adverse events, sorted by system organ class and preferred term, will be summarized by treatment group.

Allocation of TEAEs to Study Periods

TEAEs may be allocated to study periods (these will be defined in the SAP).

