13.1.3 Classification of Adverse Events

Adverse events will be classified according to the time of onset of the adverse event:

- *pre-treatment adverse event* – an adverse event that starts on or after the date the participant signed the *Informed Consent Form* and prior to the date and time of the dose of IMP.
- *treatment-emergent adverse event (TEAE)* – an adverse event that starts during or after administration of the dose of IMP, or a pre-treatment adverse event that increases in intensity or becomes serious during or after administration of the dose of IMP.

For handling of adverse events with incomplete start dates to facilitate this classification, see section 22.3.5. Note that adverse events with incomplete start dates will be classified as treatment-emergent simply if the imputed start date is on or after the date of IMP infusion, since the start time of the adverse event will not be imputed, unless the investigator in such a case has assessed that the causality to IMP is *not related - prior to IMP*.

An adverse event is considered causally related to the use of the IMP when the causality assessment by the investigator is *probable* or *possible*. If the causality assessment is missing, the adverse event is considered possibly causally related.

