13.1.5 Presentation of Treatment-emergent Adverse Events

The following summaries will be provided for the APTS:

- TEAEs by SOC and preferred term
- TEAEs by preferred term
- TEAEs by sex and preferred term
- TEAEs with an incidence $\geq 2\%$ and 5% in any treatment group by preferred term
- causally related TEAEs by SOC and preferred term
- TEAEs by severity (*mild/moderate/severe*), SOC, and preferred term
- causally related TEAEs by severity, SOC, and preferred term
- TEAEs occurring on the day of dosing after infusion start by SOC and preferred term

For TEAEs occurring on the day of dosing after infusion start, TEAEs with missing start times will also be included.

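### Start time is not required for adverse events lasting 24 hours or more, so a lasting event that began on Day 0 before the infusion can be counted as treatment-emergent and post-infusion

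*Protocol*

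**What the plan says.** **Collection.** Protocol 10.3 requires "start and stop dates (and start and stop time if the adverse event lasts less than 24 hours". Events of 24 hours or more need dates only. Protocol Panel 2 also has a row for recording, on the Adverse Event Form, "Signs and symptoms present at Screening and Baseline (before IMP administration"). Pre-infusion symptoms on the infusion day (Day 0) therefore go on the same form as later events.

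**Definitions.** Three definitions turn on the start of an event:

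- Protocol 16.9.1 defines a treatment-emergent event (TEAE) by date: "an adverse event that starts or increases in intensity on or after the date of first dose of IMP".
- SAP 13.1.3 defines it by time. A pre-treatment event starts "prior to the date and time of the dose of IMP". A TEAE is "an adverse event that starts during or after administration of the dose of IMP", or a pre-treatment event that then worsens or becomes serious.
- Protocol 10.1.3.1 includes among infusion-related reactions (IRRs) "any event occurring on the day of the IMP infusion after the infusion was started".

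**Defaults.** For events with incomplete start dates, SAP 13.1.3 assigns treatment-emergent status if the imputed date is on or after the infusion date. It makes an exception where the investigator judged the event unrelated because it preceded the product. SAP 22.3.5 says that start times are not imputed. For the table of dosing-day events after infusion start, SAP 13.1.5 says that "TEAEs with missing start times will also be included".

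**The concern.** The SAP draws its pre-treatment/TEAE boundary on Day 0 by the clock, and so does its dosing-day table. The protocol does not require the clock time for the longer events. If the time was never collected, no analysis rule can recover it.

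Three gaps in wording add to this:

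- The SAP 13.1.3 default and its exception cover incomplete dates only. An event with a complete Day 0 date and no time is not addressed.
- The causality category used in that exception is not on the scale in Protocol 10.1.2, which has only probable, possible and not related.
- The two documents define a TEAE differently.

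At stake is how clean the dosing-day safety tables are in an early trial of an intravenous antibody. Protocol 1.1.3 itself says that the relation between dose and the incidence of mechanism-related adverse events is uncertain.

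**Working it through.** The plan states no figure on this point, so there is none to reproduce. The check follows the rules through each kind of event, then gives a scale under stated assumptions.

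**Which events are misplaced**

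| Onset | Duration | Time required? | Result |
|---|---|---|---|
| Before Day 0 | Any | Not needed | The date shows it is pre-treatment |
| Day 0, before infusion | Under 24 h | Yes | The time shows it is pre-treatment under the SAP |
| Day 0, before infusion | 24 h or more | No | A TEAE by the protocol's date rule; no explicit SAP rule; if called a TEAE, it enters the post-infusion table |
| Day 0, after infusion start | 24 h or more | No | Counted as post-infusion, which is correct |
| After Day 0 | Any | Not needed | The date shows it is a TEAE |

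Only the third row can go wrong. Within it, an event that worsened or became serious after dosing is a TEAE under the SAP anyway. The infusion's own clock times are captured (Protocol 16.7), so the missing item is the start time of the event.

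**Scale**

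Inputs: planned groups of 92, 46 and 92, total 230 (Protocol 3.1). Let p be the share of patients with a third-row event. The documents give no p, so 1%, 2% and 5% are assumptions.

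Expected number = n × p. Chance of at least one = 1 − (1 − p)^n.

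| p | Expected among 230 | At least one in 46 | At least one in 92 |
|---|---|---|---|
| 1% | 2.3 | 0.37 | 0.60 |
| 2% | 4.6 | 0.61 | 0.84 |
| 5% | 11.5 | 0.91 | 0.99 |

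SAP 13.1.5 tabulates preferred terms reaching 2% in any group. In the 46-patient arm one event is enough: 1/46 = 2.17%. In a 92-patient arm it takes two with the same term: 1/92 = 1.09%, 2/92 = 2.17%.

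**Effect on a comparison**

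Suppose true dosing-day rates of 5% on active and 1% on placebo (also an assumption), and add p to both:

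- p = 1%: 6% v 2%, difference 4 points, ratio 3
- p = 3%: 8% v 4%, difference 4 points, ratio 2
- p = 5%: 10% v 6%, difference 4 points, ratio 1.7

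The true ratio is 5. The ratio shrinks and the difference does not. For counts of patients, independent overlap between true and misplaced events would multiply the difference by (1 − p): 4 × 0.95 = 3.8 points at p = 5%.

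**Is p likely to be large?**

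Take the Day 0 window before infusion as half a day and onset as constant over time (both assumptions). A 28-day screening period then holds 56 such windows. A p of 3% to 5% would imply 56 × 0.03 = 1.7 to 56 × 0.05 = 2.8 new lasting events per patient during screening, which looks too high. A p of 1% would imply 56 × 0.01 = 0.56.

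**The case against.** The strongest reply is that the plan has already chosen, openly, to err on the side of inclusion. The protocol's TEAE definition is by date, the SAP uses the date alone when a start date is imputed, and SAP 13.1.5 says that untimed TEAEs go into the dosing-day table. A reader might infer that long Day 0 events cannot be classified at all. The documents do not support that: these rules lead to a class, and the fault is that it can be the wrong one for a narrow group.

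A reader might also infer that IRRs cannot be identified for longer events. That does not follow either. Panel 2 states "Infusion-related reactions must be checked as part of the overall AE collection, during and after infusion", and Protocol 8.3 requires at least 2 hours of monitoring after the infusion. Adverse events are collected separately before and after it. Site identification of IRRs does not rest on a recorded clock time alone. SAP 13.1.10 is redacted and may hold further rules, so nothing is inferred from its absence.

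The eCRF may in part hold the needed information already. The SAP's exception implies that investigators can mark an event as preceding the product, SAP 13.1.1 lists time since infusion, and Protocol 10.3 does not forbid entering a time for a longer event. SAP 13.1.4 also lists every adverse event with a TEAE flag, so individual cases stay open to review.

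Most of this stands and limits the size of the point. It does not remove it. The protocol does not require the time, the exception is worded for incomplete dates only, and a listing does not correct a summary table.

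**Conclusion.** The point holds in a limited form. Under the rules as written, an adverse event that began on Day 0 before the infusion and lasted 24 hours or more can be reported as treatment-emergent and as occurring after infusion start.

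The size is unknown and probably small. It depends on p, for which the documents give no value. The effect is a modest inflation of Day 0 counts and of low-incidence TEAE tables, most visible in the 46-patient arm.

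A reader might infer that the rule biases or hides the comparison of active with placebo. The documents do not support that. Pre-infusion onset cannot depend on treatment, and recording is blinded, so all arms are inflated alike. Ratios shrink and noise rises, but absolute differences are essentially unchanged in expectation. The efficacy analyses are not touched.

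It is still worth correcting, because a time that is not collected on the day cannot be supplied later by the SAP.

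**What to change.** - **Protocol 10.3:** require the start time, or a field for onset before or after the start of infusion, for every adverse event with onset on the infusion day, whatever its duration.
- **SAP 13.1.3:** classify all Day 0 events by that information, and say explicitly what happens to a complete date without a time. Align the TEAE definition with Protocol 16.9.1, and match the causality category used in the exception to the scale in Protocol 10.1.2, or replace it with the new field.
- **SAP 13.1.5:** limit the inclusion of untimed events to those where the before/after information is also missing, and report how many there are.

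The cost is one extra eCRF field for Day 0 events and a few sentences of SAP text. The patient is on site during the infusion and for at least 2 hours after it, so the information can be obtained at the visit.

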10.4 Reporting Serious Adverse Events

The investigator must report SAEs to Lundbeck immediately (within 24 hours) after becoming aware of them by completing a *Serious Adverse Event Form*.

The initial *Serious Adverse Event Form* must contain as much information as possible and, if more information about the patient's condition becomes available, the *Serious Adverse Event Form* must be updated with the additional information.

If the investigator cannot report the SAE in Rave[®], then he or she must complete and sign the Serious Adverse Event Fallback Form and send it to:

[contact]
email: [contact]

Lundbeck will assume responsibility for reporting SAEs to the authorities in accordance with local requirements.

It is the investigator's responsibility to be familiar with local requirements regarding reporting SAEs to the EC or IRB and to act accordingly.

Lundbeck will assume responsibility for reporting sudden unexpected adverse reactions (SUSARs) to the authorities in accordance with local requirements. In those Member States of the European Union that have implemented the European Union Clinical Trials Directive⁶¹ and in Norway, Liechtenstein, and Iceland, that is, in the countries where unblinded expedited safety reporting is required, Lundbeck will also assume responsibility for reporting SUSARs to the ECs.

Lundbeck will assess the expectedness of SAEs and inform the investigator(s) about SUSARs in the blinded SUSAR listings.

10.5 Treatment and Follow-up of Adverse Events

Patients with adverse events must be treated in accordance with usual clinical practice at the discretion of the investigator.

The investigator must follow up on non-serious adverse events until resolution or the Safety Follow-up Visit/Contact, whichever comes first. At the Safety Follow-up Visit/Contact, information on new SAEs, if any, and stop dates for previously reported adverse events must be recorded.

The investigator must follow up on all SAEs until the patient has recovered, stabilized, or recovered with sequelae, and report to Lundbeck all relevant new information using the same procedures and timelines as those for the initial *Serious Adverse Event Form*.

SAEs that are spontaneously reported by a patient to the investigator after the Safety Follow-up Visit/Contact must be handled in the same manner as SAEs that occur during the study. These SAEs will be recorded in the Lundbeck safety database.

The investigator must follow up on patients with a clinically significant out-of-range clinical safety laboratory test value at the Primary Outcome or Withdrawal Visit for up to 12 weeks. If the clinically significant out-of-range clinical safety laboratory test value has not normalized or stabilized or a diagnosis or a reasonable explanation has not been established

by the Safety Follow-up Visit, the investigator must decide whether further follow-up visits are required (this may include an additional medical examination and/or additional blood sampling). If further follow-up visits are made, these must be documented in the patient's medical records and not in the eCRF.

10.6 Data Monitoring Committee

The DMC will consist of medical doctors with speciality relevant to the fields of neurology, immunology and rheumatology. The DMC will monitor safety data on an ongoing basis in addition to cumulative safety data. The DMC will be informed to what extent the data and analyses provided to them have been quality controlled. Members of the DMC will not be involved in other study-related tasks. The DMC procedures are described in the *DMC Charter*.

11 Data Handling and Record Keeping

11.1 Data Collection

11.1.1 Electronic Case Report Forms

eCRFs will be used to collect all the data related to the study, except the external data described in section 11.1.3.

The eCRFs use third party software (Rave[®]) to capture data via an online system on a computer. When the investigator enters data in the eCRF (ideally during the visit or as soon as possible [<3 days] thereafter), the data will be recorded electronically in a central database over encrypted lines, and all entries and modifications to the data will be logged in an audit trail. Access to the system will only be granted after appropriate and documented training. Written instructions for using the system will be provided along with the training.

Electronic signatures will be used where signatures are required on pages and/or visits. Automated data entry checks will be implemented where appropriate; other data will be reviewed and evaluated for accuracy by the sponsor and/or representatives from PPD. All entries, corrections, and changes must be made by the investigator or a delegate.

